**VERSION DATE**

**06/04/2018**

**SPECIFIC AIMS**

Concisely state the objectives of the study and the hypothesis being tested.

**Hypothesis 1:** Patients with insomnia have longer, more consolidated sleep after treatment with Bioboosti.

**Specific Aim 1:** This hypothesis will be tested in a prospective study, using within subject comparisons, whereby sleep measures before treatment are compared to those after treatment.

**Hypothesis 2:** Sleep improvement will lead to a lesser subjective daytime sleepiness and reduction in migraine frequency/intensity.

**Specific Aim 2:** This hypothesis will be tested by comparing subjective measures of sleepiness, measured by standard instruments (Epworth sleepiness scale score, ESS, Karolinska sleepiness scale KSS), relative to total sleep time and wake after sleep onset. Migraine frequency and intensity will be recorded using standardized headache diaries.

**Exploratory aim:** To evaluate the physiological mechanisms, by which Bioboosti may exert its effect on sleep and overall health. This will be accomplished by a measurement of hormones directly affecting sleep and

sympathetic autonomic nervous system (urinary cortisol and catecholamines), immune, as well as autonomic function.

### **Arm 1**

**Aim 1:** To test the hypothesis that treatment with BioBoosti has sustained efficacy in treating insomnia.

Our primary endpoint would be insomnia symptoms after 1 year of BioBoosti use as compared to initial symptoms (prior to starting treatment).

Measurement of insomnia will be done in serial comparisons every 3 months for ISI, TST (Total Sleep Time), WASO (Wake After Sleep Onset), as well as PSQI at year 1. We will use repeated measures ANOVA to compare ISI, TST, WASO, at months 3, 6, 9, and 12 and a T-test to compare PSQI at baseline to that after 1 year.

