We do not anticipate all 20 subjects to participate however, interested enrolled subjects will also be offered to continue the treatment for one year for the evaluation of sustained efficacy of BioBoosti as Insomnia Treatment. We *anticipate* enrolling up to 20 subjects at BWH and Faulkner Hospitals.

The study will also look at the effects of the BioBoosti device on sleep and recurrence of headache for patients who have been diagnosed with both insomnia and migraine. The study protocol remains the same besides the treatment with BioBoosti will be for 4 weeks to allow adequate headache assessment.

We anticipate enrolling 20 additional subjects with insomnia and comorbid migraine at Brigham and Women's and Faulkner Hospitals.

Briefly describe study procedures. Include any local site restrictions, for example, "Subjects enrolled at Partners will not participate in the pharmacokinetic portion of the study." Describe study endpoints.

The BWH and FH sleep clinics will be screened for follow-up patients with insomnia. Study staff will notify the treating physician to inform them of a potential subject. The treating physician will first introduce the study to the potential subject. If the subject gives permission and would like to obtain more information regarding the study, study staff will approach them and provide them with a copy of the consent form to review. Study staff may also contact the subject by phone to explain the study and recruit if it is more convenient for the subject. Study staff and a physician investigator will be available to answer all questions. If the potential subject is interested in participating in the study, the Principal Investigator will consult with the treating physician prior to enrolling the subject. If the subject decides to enroll in the study when approached in the clinic, we will proceed with Visit 1 (Enrollment Visit) that same day. The physician investigator will be available to speak with subjects during the consent process.

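### The 1-year primary endpoint is tested through four measures with no primary variable or success rule, and three of the four tests leave out baseline

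*Combined protocol and SAP*

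**What the plan says.** Specific Aims, Arm 1, contains the only use of the term primary endpoint for this trial: "Our primary endpoint would be insomnia symptoms after 1 year of BioBoosti use as compared to initial symptoms". The endpoint is a concept. No scale or recording is named as its measure.

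The same paragraph lists ISI, TST and WASO every three months, plus PSQI at year 1, as the measurement of insomnia. The analysis has two parts:

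- "We will use repeated measures ANOVA to compare ISI, TST, WASO, at months 3, 6, 9, and 12"
- "a T-test to compare PSQI at baseline to that after 1 year"

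The document gives no significance level, sidedness, hierarchy, multiplicity adjustment or rule for when the endpoint is met.

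The opening Specific Aim 1 is a separate statement. Its hypothesis is "Patients with insomnia have longer, more consolidated sleep after treatment with Bioboosti", tested by a within-subject design in which "sleep measures before treatment are compared to those after treatment". It gives no time point. Research Design and Methods and the insomnia Treatment phase and Visit 4 make it two weeks. The 1-year phase is an optional continuation with fresh consent, and Research Design and Methods says of it: "We do not anticipate all 20 subjects to participate however".

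**The concern.** There are two gaps, both in the Arm 1 paragraph.

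1. **No deciding variable.** Four measures stand for one primary endpoint on an equal footing. Nothing tells the analyst which one decides, or whether one, several or all must be significant. A single favourable result out of four could be reported as meeting the primary endpoint, and nothing in the plan would contradict that.
2. **The test does not match the contrast.** The endpoint compares 1 year with the pre-treatment state. The ANOVAs list four follow-up months and no baseline, so they ask whether the follow-up months differ from one another.

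At stake is whether a positive or negative statement about the primary endpoint can be interpreted. The aim is worded as a test of a hypothesis and significance tests are specified, so the error rate of that claim matters even at this size.

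**Working it through.** **Plan's own figure.** There is none to reproduce. The document states no alpha, power or sample-size derivation.

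**Inputs from the document (Arm 1).** Four measures: three repeated measures ANOVAs (ISI, TST, WASO, read as one each) and one t-test (PSQI). Planned sample of 20, with fewer expected at 1 year (Research Design and Methods).

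**Assumptions, because the document is silent.** Two-sided 0.05 per test; no adjustment; any one significant result counts as success; correlation between measures unknown, so a range is shown.

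**Step 1: independent tests.** P(at least one false positive) = 1 - (1 - 0.05)^4 = 1 - 0.8145 = 0.185.

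**Step 2: correlated tests.** Four equally correlated two-sided z-tests at 0.05, 1,000,000 simulated draws:

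| Correlation | Chance of at least one false positive |
|---|---|
| 0 | 18.6% |
| 0.3 | 17.4% |
| 0.5 | 15.5% |
| 0.7 | 13.1% |
| 0.8 | 11.4% |
| 0.9 | 9.4% |

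**Step 3: the plan's own mix of tests.** Three ANOVA F-tests and one paired t-test, 20,000 simulated trials per setting, with an assumed within-subject correlation of 0.5 over time:

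| n | ANOVA time points | Corr. 0 | Corr. 0.5 | Corr. 0.7 |
|---|---|---|---|---|
| 10 | months 3-12 | 18.1% | 17.2% | 15.6% |
| 10 | baseline + months 3-12 | 18.2% | 16.9% | 15.1% |
| 20 | months 3-12 | 18.6% | 17.0% | 15.4% |
| 20 | baseline + months 3-12 | 18.6% | 16.9% | 14.9% |

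Steps 2 and 3 together give about 13-16% at correlation 0.7. The figure hardly changes with n or with whether baseline is in the ANOVA.

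**Step 4: other success rules.** If all four had to be significant, the error would be no more than 5% without adjustment. With Bonferroni, 0.05/4 = 0.0125 per test, and 1 - (1 - 0.0125)^4 = 0.049 if independent.

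**Step 5: contrast tested against contrast stated.**

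| Measure | Test as written | Compares 1 year with pre-treatment? |
|---|---|---|
| ISI, TST, WASO | ANOVA over months 3, 6, 9, 12 | No |
| PSQI | t-test, baseline against 1 year | Yes |

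If the device gave a benefit by month 3 that then held steady, the four follow-up means would be equal and the F-test would have nothing to detect. If the benefit waned, the F-test could be significant. Neither outcome answers the stated question.

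**The case against.** **The figure depends on a reading the plan does not state.** This is correct. Neither the 5% level nor the any-one-counts rule is in the document, and under an all-four rule there is no inflation. What survives is that the plan is silent on the rule, so the figure has to be given as conditional.

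**Only the PSQI t-test addresses the stated contrast, so PSQI might be taken as the primary.** Nothing says so. The Arm 1 paragraph presents the other three as measures of the same endpoint.

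**It is a pilot in 20 or fewer subjects.** Background and Significance does call it one. Presenting every measure as an estimate with a confidence interval, with no significance claim, would also settle the error-rate point. As written, though, the aim is a hypothesis test.

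**ISI is not the obvious choice.** Hypothesis 1 concerns longer and more consolidated sleep, which points to TST and WASO, and ISI is self-reported in a single-arm study. The trade-off is real. The case for ISI is that the Arm 1 endpoint is worded as symptoms and that the protocol describes ISI as measuring insomnia severity.

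**A stronger reading that a reader might infer.** Because Aim 1 appears both as a short before-after comparison and as a 1-year objective, one could say that the primary time point is also open and count eight tests. That would give 1 - 0.95^8 = 33.7% if independent and 19.1% at correlation 0.7. The document does not support this. The primary endpoint is named only under Arm 1, where its time is fixed at 1 year. The opening Specific Aim 1 claims no primary status, and the 1-year phase is a separate continuation. The four-week comparison belongs to the migraine cohort under Aim 2 and is not a rival Aim 1.

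**Conclusion.** The point holds in conditional form. The primary variable and the success rule are missing. At an assumed two-sided 0.05 per test with any one result sufficient, the chance of at least one false positive is 18.5% for independent measures, about 13-16% at correlation 0.7, and about 9% at 0.9. It would be wrong to say that a stated 5% level is exceeded, because the document states none.

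The missing baseline needs no assumption beyond reading the listed months literally: three of the four tests do not address the stated contrast.

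The shared Aim 1 label is a drafting matter and contributes nothing to these figures. The whole point concerns what may be claimed from the trial, not subject safety, and should be settled before the 1-year data are analysed.

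**What to change.** In Specific Aims, Arm 1:

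1. Name one primary variable and contrast: change in ISI from pre-treatment baseline to month 12. ISI is already collected at both times (For Insomnia, Visit 2; Visit at 12th month). State the significance level and sidedness.
2. Add baseline to the repeated measures models for ISI, TST and WASO, and specify the baseline-to-month-12 contrast within them.
3. Report TST, WASO and PSQI as secondary, with confidence intervals and no primary claim. If all four are to stay primary, apply a Holm adjustment (0.05/4 = 0.0125 for the smallest p-value, then 0.05/3, 0.05/2 and 0.05).
4. Give the two-week before-after comparison in the opening Specific Aim 1 its own name, distinct from the 1-year objective.

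This costs a few sentences and needs no new data. The downsides are that a lone positive TST, WASO or PSQI result could no longer be called a primary success, and that a self-reported scale would be the sole primary in a single-arm study. If the investigators prefer TST or WASO because of Hypothesis 1, naming that one measure in advance would close the error-rate gap equally well. They would then also need to say which recording it comes from, since the plan uses EEG, actiwatch and sleep logs before treatment and lists no EEG at the 1-year-phase visits.

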### For Insomnia

#### **Visit 1**

Subjects who are interested in participating will sign the consent form. A screening physical exam will be done, and vital signs (blood pressure, heart rate, pulse rate, respiratory rate) will be measured. Pregnancy test will be done for women of childbearing potential.

Subjects will go home with sleep logs, which are subject records of when they go to sleep and wake up. They will also be given an actiwatch to wear, as an objective measure of sleep and wake periods.

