#### **Visit 2**

Subjects will be scheduled for a follow up at FH.

Subjective sleep symptoms will be evaluated using validated instruments, including Pittsburgh Sleep Quality Inventory (PSQI), and severity of insomnia - Insomnia Severity Index (ISI), and daytime sleepiness Epworth Sleepiness Scale (ESS), and daily visual analog scale (Karolinska sleepiness scale, KSS).

Objective sleep assessment will be performed using ambulatory 72 hour EEG, using sleep montage per standard AASM criteria, and scored by a registered polysomnography technologist using AASM guidelines. If the subject expresses hesitation because of the 72 hour EEG, then a 48 hour EEG will be offered.

Assessment of sympathetic autonomic nervous system function will be done by measuring cortisol and catecholamine levels using standard assays.

Subjects will continue to wear the actiwatch and complete sleep logs daily.

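### The repeated measures ANOVA for ISI, TST and WASO leaves out baseline, so it does not test the primary comparison of 1 year with before treatment

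*Combined protocol and SAP*

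**What the plan says.** Specific Aims, Arm 1, Aim 1 concerns sustained efficacy over a year of device use. It defines the primary endpoint as "insomnia symptoms after 1 year of BioBoosti use as compared to initial symptoms (prior to starting treatment". It lists ISI, TST, WASO and PSQI together as the measures of insomnia and does not single one out as primary.

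One sentence then gives the tests. For three measures: "We will use repeated measures ANOVA to compare ISI, TST, WASO, at months 3, 6, 9, and 12". For the fourth: "a T-test to compare PSQI at baseline to that after 1 year".

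The general Specific Aim 1 describes a within-subject design in which "sleep measures before treatment are compared to those after treatment", but names no statistic. No other section names a test of ISI, TST or WASO against baseline.

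The Sustained Efficacy Phase section has treatment continuing through the year, so months 3, 6, 9 and 12 are all on treatment. On numbers, Research Design and Methods allows up to 20 subjects for this phase and adds: "We do not anticipate all 20 subjects to participate".

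**The concern.** The question is whether patients are better at 1 year than before they started. A comparison confined to months 3 to 12 contains no pre-treatment value, so it cannot estimate that difference. It also runs against the aim. The result the investigators hope for, an early gain that lasts, makes the four means equal and the ANOVA non-significant. A gain that fades makes them unequal and the ANOVA significant. A reader who takes a significant F as support for sustained efficacy, or a non-significant F as failure, could draw the wrong conclusion on three of the four insomnia measures.

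**Working it through.** **No figure to reproduce.** The document gives no significance level, power, effect size, SD or sample-size derivation. The main step is therefore to read the stated model; the numbers after it are illustrative.

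**Step 1: the hypotheses.** Write μ0 for the pre-treatment mean and μ3, μ6, μ9, μ12 for the follow-up means.

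- Primary comparison as defined: μ12 − μ0.
- Null hypothesis of the ANOVA as written: μ3 = μ6 = μ9 = μ12.

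μ0 does not appear in the second line. Adding any constant to all four follow-up values leaves F unchanged. On one simulated data set (n = 20, SD 5, correlation 0.5), shifting all four visits by 0, 3, 5 or 10 points gave F(3,57) = 1.424, p = 0.245 each time. This step needs no assumed effect size or SD.

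**Step 2: how often each test rejects.** Assumed inputs, none from the document: SD 5, exchangeable within-subject correlation ρ = 0.3 to 0.7, two-sided 5% tests, complete data, n = 10 or 20, effect 5 or 3 points. Only effect divided by SD matters, so these are effects of 1.0 and 0.6 SD and can be read for TST and WASO on that scale.

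- ANOVA as written: noncentral F with 3 and 3(n − 1) df and noncentrality λ = n·Σ(μj − μ̄)² / [SD²(1 − ρ)], summed over the four follow-up months.
- Month 12 minus baseline: paired t with n − 1 df and noncentrality δ = √n·(μ12 − μ0) / [SD·√(2(1 − ρ))].

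Profiles at months 3, 6, 9, 12, as multiples of the effect: steady 1, 1, 1, 1; half lost 1, 5/6, 2/3, 1/2; fully lost 1, 2/3, 1/3, 0.

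Worked cell (5 points, n = 20, ρ = 0.5):

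- Steady: Σ(μj − μ̄)² = 0, so λ = 0 and the ANOVA rejects 5%. δ = √20 × 5 / (5 × √1) = 4.47, so the contrast rejects 99%.
- Fully lost: means 5, 3.33, 1.67, 0, so Σ(μj − μ̄)² = 13.89. λ = 20 × 13.89 / (25 × 0.5) = 22.2, so the ANOVA rejects 98%. δ = 0, so the contrast rejects 5%.

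Ranges over ρ = 0.3 to 0.7:

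| Profile | Effect | n | ANOVA as written | Month 12 − baseline |
|---|---|---|---|---|
| Steady | 5 | 10 | 5% | 66–95% |
| Steady | 5 | 20 | 5% | 95–100% |
| Steady | 3 | 10 | 5% | 30–59% |
| Steady | 3 | 20 | 5% | 58–91% |
| Half lost | 5 | 10 | 17–36% | 22–45% |
| Half lost | 5 | 20 | 33–69% | 43–78% |
| Half lost | 3 | 10 | 9–15% | 11–20% |
| Half lost | 3 | 20 | 14–28% | 19–38% |
| Fully lost | 5 | 10 | 58–93% | 5% |
| Fully lost | 5 | 20 | 91–100% | 5% |
| Fully lost | 3 | 10 | 23–50% | 5% |
| Fully lost | 3 | 20 | 47–85% | 5% |

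Simulation with 20,000 replicates per cell agreed within 1 percentage point for the 5-point cells at ρ = 0.3 and 0.7.

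**Step 3: is adding baseline enough?** No. In a separate simulation (1 SD effect fully lost by month 12, ρ = 0.5), a five-level omnibus F that included baseline rejected 85% of the time at n = 10 and over 99% at n = 20, although month 12 equalled baseline. The contrast itself has to be named.

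**Step 4: do the baseline data exist?**

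- ISI: yes. It is taken at Visit 2, before the device is given at Visit 3, and again at months 3, 6, 9 and 12.
- TST and WASO: the source is not named. EEG is done around Visits 2 and 4 but is not listed at the one-year visits. Sleep logs and the actiwatch span both periods; at Visit 1, "They will also be given an actiwatch to wear, as an objective measure of sleep and wake periods". In follow-up, actiwatch wear begins one month before each visit.
- Actiwatch baseline window: the insomnia Visit 2 text says only "Subjects will be scheduled for a follow up at FH", with no interval, whereas the migraine group's Visit 2 is one month after Visit 1.

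**The case against.** The strongest reply is that this is loose wording. The primary endpoint, defined just before the ANOVA sentence, is a comparison with initial symptoms, and the general aim describes before-after testing. The month list may simply be the follow-up schedule, with baseline taken as understood. That is possible. But the test sentence lists its time points explicitly and names baseline for PSQI alone, so an analyst following it would leave baseline out. Even if baseline were understood, Step 3 shows that the omnibus test would not isolate the 1-year comparison.

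A second reply is that PSQI already carries the primary comparison in a small pilot with an optional extension. PSQI does have the right test, but the plan does not make it the sole primary measure, and a small sample does not excuse testing a different question.

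Three points on the other side stand:

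- Comparing months 3 to 12 does bear on durability and is worth keeping as a secondary analysis.
- The baseline window is loosely bounded. Visit 5 of the insomnia schedule puts testing at about one month per patient. Taking 28 to 31 days, less 14 days of treatment and two 72-hour EEGs (6 days), leaves roughly 8 to 11 days. That is still not a stated window, and it is shorter than the month used in follow-up.
- Naming the contrast for three measures beside the PSQI t-test does not settle which measure is primary or how four tests are handled together. That is a separate matter.

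**Conclusion.** The concern holds and should be fixed before analysis. As written, the stated test for ISI, TST and WASO does not address the stated primary comparison; only PSQI has a named test against baseline. This follows from the time points listed and depends on no assumed effect, SD or correlation.

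The rejection rates do rest on assumptions: a 5% level, exchangeable correlation, complete data, and effects of 0.6 or 1.0 SD. Across that grid the ANOVA rejects 5% of the time for a steady benefit and 23 to 100% for a benefit fully lost by month 12. The size varies, but the direction does not: the more of the early benefit is lost, the more likely the ANOVA is to be significant. The authors may well have meant to include baseline, but the plan does not say so.

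**What to change.** In Arm 1, Aim 1:

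1. Add the pre-treatment value as a time level in the repeated measures analysis of ISI, TST and WASO. A mixed model is one option.
2. Name month 12 minus baseline, not the omnibus F, as the test of the primary comparison for these measures. For ISI, define baseline as the Visit 2 value.
3. Keep the comparison among months 3 to 12 as a secondary description of durability.
4. Name one source for TST and WASO and use it at baseline and at every follow-up. The actiwatch is the objective source available in both periods; sleep logs also span both. If the actiwatch is chosen, state the baseline window within the wear from Visit 1 to Visit 3.

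If baseline was always intended, the same wording makes that explicit. The cost is a few sentences of analysis text. Pre-treatment ISI, actiwatch and sleep-log data are already collected, so no new data, visits or patients are needed.

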### **Treatment phase**

There will be two weeks of treatment with Bioboosti. Subjects will be asked to use the device once a day, at approximately one hour prior to initiation of habitual sleep time. They will complete up to 6 therapy cycles. A therapy cycle consists of placing the Bioboosti on the Laogong point, which is located at the center of the palm. The device will remain there for 8 minutes, and this counts as 1 cycle. When the light on the device changes, it indicates that 8 minutes have passed, and a cycle is completed. The subject will then remove the device and replace it on the Laogong point of the other hand. The subject will repeat this up to 6 times, alternating the treatment cycles between one hand to another.

They will complete sleep logs for two weeks, as well as wear the actiwatch.

During this time, subjects should not drive while using the Bioboosti. They will also be advised to maintain a healthy lifestyle, as is done during clinic visits (light diet, regular exercise, smoking cessation, abstinence and sufficient sleep), but these are not terms of exclusion from the study.

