### **Visit 4**

Subjects will return after the two weeks of treatment. They will return the completed sleep logs.

Subjective sleep symptoms will be evaluated using validated instruments including, Pittsburgh Sleep Quality Inventory (PSQI), and severity of insomnia - Insomnia Severity Index (ISI), and daytime sleepiness Epworth Sleepiness Scale (ESS), and daily visual analog scale (Karolinska sleepiness scale, KSS).

Objective sleep assessment will be performed using ambulatory 72 hour EEG, using sleep montage per standard AASM criteria, and scored by a registered polysomnography technologist using AASM guidelines. If the subject expresses hesitation because of the 72 hour EEG, then a 48 hour EEG will be offered.

Assessment of urine cortisol and catecholamines will be done as a measure of sympathetic function.

Subjects will continue to wear the actiwatch and complete sleep logs daily.

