### **Visit 5**

Subjects will return for the EEG to be removed. They will return the Bioboosti, actiwatch and completed sleep logs.

The Bioboosti devices will be checked on their return to the study staff. If it is determined that the device is not functioning properly, the participant will be asked to redo the study.

Testing of each patient requires about one month as outlined above. With efficient recruitment and minimal attrition rate, 20 participants can complete the study.

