### **Sustained Efficacy Phase**

Subjects participating in the study will also be asked if they are interested in the long-term use of BioBoosti device. In that case, they will be consented again to go forward with the long-term use. At the end of this process, they will be given sleep and headache logs.

They will be offered to continue the treatment for one year with regular follow-up. One month prior to each follow-up they will be asked to use the actiwatch to objectively evaluate the sleep patterns. They will either pick up the device or will be offered a home visit for the actiwatch use.

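### Arm 1 asks whether efficacy is sustained, but neither named test uses the two-week response, and the ANOVA also leaves out baseline

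*Combined protocol and SAP*

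**What the plan says.** All references are to the combined protocol and SAP.

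- **Specific Aims, Arm 1.** The aim is "To test the hypothesis that treatment with BioBoosti has sustained efficacy in treating insomnia". The reference point is pre-treatment: "Our primary endpoint would be insomnia symptoms after 1 year of BioBoosti use as compared to initial symptoms (prior to starting treatment". Two tests are named. The first reads "We will use repeated measures ANOVA to compare ISI, TST, WASO, at months 3, 6, 9, and 12". The second, which concerns PSQI alone, is "a T-test to compare PSQI at baseline to that after 1 year". The section gives no definition of sustained, no retention margin and no statement of which result would support the hypothesis.
- **For Insomnia, Treatment phase and Visit 4.** "There will be two weeks of treatment with Bioboosti", and then "Subjects will return after the two weeks of treatment". Visit 4 collects ISI and PSQI, among other measures, and starts an ambulatory EEG. The actiwatch and sleep logs run through treatment and continue after Visit 4.
- **For Insomnia, Visit 5.** "They will return the Bioboosti, actiwatch and completed sleep logs".
- **Sustained Efficacy Phase.** After a second consent, "They will be offered to continue the treatment for one year with regular follow-up". The actiwatch is worn in the month before each follow-up. ISI and PSQI are repeated at months 3, 6, 9 and 12. No EEG is listed.
- **Research Design and Methods.** Twenty subjects are planned, and not all of them are expected to enter the one-year phase.

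**The concern.** Durability has two parts: whether there is still a benefit over baseline at one year, and whether the early response has held. The named tests address the first part for PSQI only and do not address the second for any measure. The response that is supposed to be sustained is measured at two weeks, then left out of the analysis. Any fading of a novelty or expectation effect before month 3, followed by a flat course, falls outside both tests.

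The ANOVA has a second gap. With four on-treatment points and no baseline, it asks only whether months 3 to 12 differ among themselves. It therefore does not test the stated primary comparison on ISI, TST or WASO.

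The device hand-back at Visit 5 makes the early interval harder to read. Treatment is then described as continuing, but the documents do not say how long subjects are without the device or from which date the months are counted.

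**Working it through.** The plan states no sample-size calculation, alpha, effect size or SD for Arm 1, so there is no figure to reproduce.

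**Step 1: what each test depends on.** Write b for baseline, v for Visit 4, and m3, m6, m9, m12 for follow-up. The ANOVA uses only m3 to m12. The T-test uses only b and m12 (PSQI). Neither contains v, so two courses that differ only in v give identical results.

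Illustration with assumed means on one scale:

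| Course | b | v | m3 to m12 | Spread over m3 to m12 | b − m12 | m12 − v |
|---|---|---|---|---|---|---|
| Kept | 20 | 15 | 15 | 0 | 5 | 0 |
| Half lost | 20 | 10 | 15 | 0 | 5 | +5 |
| Late gain only | 20 | 20 | 15 | 0 | 5 | −5 |
| All lost | 20 | 10 | 20 | 0 | 0 | +10 |

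The ANOVA sees only the spread column, which is 0 in every row. The b − m12 column is formally tested only for PSQI, and it cannot separate the first three rows. Only m12 − v separates all four.

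**Step 2: how often this happens.** Assumptions, none of them in the documents: two-sided alpha 0.05; complete data; equal correlation between time points (0.5 or 0.7); a baseline-to-Visit-4 gain of d cross-sectional SDs, half lost by month 3 and flat afterwards; PSQI following the same course as ISI; n from 8 to 20. ANOVA results and joint chances come from 20,000 simulated trials per setting.

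PSQI test: standardised paired difference = (d/2)/√(2(1 − correlation)). For d = 1.0 and correlation 0.5 this is 0.5/1 = 0.5. With n = 20 the noncentrality is 0.5 × √20 = 2.24, and power is 57%.

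Results at correlation 0.5:

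| n | d | ANOVA m3–m12 not significant | PSQI test significant | Both | ANOVA with Visit 4 added, significant |
|---|---|---|---|---|---|
| 10 | 0.5 | 95% | 11% | 10% | 10% |
| 10 | 1.0 | 95% | 29% | 28% | 28% |
| 10 | 1.5 | 95% | 56% | 54% | 59% |
| 10 | 2.0 | 95% | 80% | 77% | 87% |
| 20 | 0.5 | 95% | 19% | 18% | 16% |
| 20 | 1.0 | 95% | 57% | 54% | 57% |
| 20 | 1.5 | 95% | 89% | 85% | 93% |
| 20 | 2.0 | 95% | 99% | 94% | >99% |

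At correlation 0.7 and n = 20, the Both column becomes 27%, 75%, 94% and 95%. Over all settings it runs from about 9% (n = 8, d = 0.5, correlation 0.5) to 95%. Complete loss by month 3 also leaves the ANOVA non-significant about 95% of the time (n = 10 and 20), because the four means are then equal.

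**Step 3: precision of the added contrast.** The 95% half-width for m12 − v, in SD units, is t × √(2(1 − correlation))/√n. At correlation 0.5:

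- n = 20: 2.093/√20 = 0.47
- n = 10: 2.262/√10 = 0.72
- n = 8: 2.365/√8 = 0.84

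At correlation 0.7, multiply by √0.6 = 0.775, giving 0.36, 0.55 and 0.65. For comparison, losing half of a 1.0 SD gain is a change of 0.5 SD.

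**The case against.** The strongest reply is that the plan does what it says. The endpoint is 1 year against symptoms before treatment, and a smaller benefit still present at one year meets it. This stands: retention of the early gain is an added question, and the primary comparison should stay as it is. It does not close the gap, because the hypothesis is about sustained efficacy and the ANOVA as listed does not make even the endpoint comparison.

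A second reply is that Specific Aim 1 already plans a before-and-after comparison at two weeks, so an absent early response would be seen there. That is fair, and the design can separate these courses because the data exist. But that analysis is not linked to the one-year follow-up, and only volunteers continue. Retention has to be measured within those same subjects.

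A third reply is that the early interval is not unobserved. Sleep logs are handed out on entry to the one-year phase and returned at month 3, and the actiwatch is worn in the month before that visit. This also stands: only ISI and PSQI are unmeasured between Visit 4 and month 3. If months run from first use, that is about 13 − 2 = 11 weeks. If they run from the start of the one-year phase, it is longer.

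A reader might infer that a half-lost effect would pass both tests and be reported as sustained. The documents do not support this. They set no pass rule, do not say that a non-significant ANOVA counts as success, and name a baseline-to-1-year test for PSQI only.

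**Conclusion.** The point holds as a blind spot in the analysis. Neither named test can distinguish an effect that is kept from one that partly faded before month 3 and then stayed flat. That follows from the listed time points and needs no assumption. For ISI, TST and WASO the ANOVA would also miss complete loss by month 3, apart from its 5% false-positive rate under the equal-correlation model.

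How often a half-lost effect would give a flat ANOVA together with a significant PSQI result cannot be fixed from the documents. The 9% to 95% range rests on assumed effect size, correlation, alpha and numbers, and on PSQI moving with ISI. A wrong conclusion is possible but not established. The improvement is cheap and leaves the primary endpoint unchanged.

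**What to change.** In Specific Aims, Arm 1:

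1. Fit the repeated-measures model to baseline, Visit 4 and months 3, 6, 9 and 12, for ISI, PSQI and actiwatch TST and WASO, in the subjects who enter the one-year phase. Use the actiwatch throughout, since no EEG is listed in that phase.
2. Keep month 12 versus baseline as the primary contrast.
3. Name month 12 minus Visit 4 as the supporting durability contrast, reported as a mean difference with its 95% confidence interval. Do not rely on the overall time effect, because a change from baseline alone can make it significant. Do not report a share of gain kept: it is undefined when there is no early gain (5/0 in the late-gain row) and unstable when the early gain is small.
4. Say what result will be described as sustained.
5. Reconcile Visit 5, where the device is returned, with the Sustained Efficacy Phase, where treatment is said to continue. State the start of the month count and record days off device.

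The cost is revised wording, added time points from data already collected, and the recorded dates. No new visit is needed. Two downsides should be stated in the plan. The interval will be wide with fewer than 20 subjects: at d = 0.5, adding Visit 4 makes the ANOVA significant only 8% to 26% of the time for n from 8 to 20. And because continuation is voluntary, if early responders are the ones who stay, regression to the mean can look like loss.
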